12.1.3.4 INJECTION SITE REACTIONS

The investigator should assess the injection sites at each scheduled visit for:

- Pain, tenderness, erythema, and induration severity (Table 5)
- Erythema and induration: record the maximum linear diameter
- Blisters, ulceration, necrosis: record the maximum linear diameter and severity
- Lymphadenopathy

In addition, the investigator will, whenever possible, take de-identified photos of the injection site reaction (ISR).

Injection site reactions should be recorded as AEs per Section 12.1 and Section 12.3, and recorded on the ISR specific eCRF and AE eCRF as appropriate.

Table 5 Grading the Severity of Local Injection Site Reactions

Local Reaction to Injectable Product	Grade 1 (Mild)	Grade 2 (Moderate)	Grade 3 (Severe)	Grade 4 (Potentially Life Threatening)
Pain	Does not interfere with activity	Repeated use of non-narcotic pain reliever >24 hours or interferes with activity	Any use of narcotic pain reliever or prevents daily activity	Emergency room visit or hospitalization
Tenderness	Mild discomfort to touch	Discomfort with movement	Significant discomfort at rest	Emergency room visit or hospitalization
Erythema/redness	2.5 to 5.0 cm	5.1 to 10.0 cm	>10.0 cm	Necrosis or exfoliative dermatitis
Induration/swelling	2.5 to 5.0 cm and does not interfere with activity	5.1 to 10.0 cm or interferes with activity	>10.0 cm or prevents daily activity	Necrosis

12.1.3.5 INFECTION

All subjects should be monitored for signs and symptoms of *Neisseria meningitidis* infection. Subjects are monitored every 2 weeks for adverse events.

To reduce the risk of infection, during the screening period, all subjects must have a negative result for *Neisseria meningitidis* colonization via throat swab prior to study entry. All Cohort A (Naïve) subjects who have not been previously vaccinated must be vaccinated against *Neisseria meningitidis* and receive ciprofloxacin for 14 days of starting with the first dose of RA101495 at the Day 1 Visit. A booster vaccination should be administered as clinically indicated, consistent with local standard of care. All cohort B (Switch) subjects must have documentation of prior *Neisseria meningitidis* vaccination (and booster if appropriate) prior to study entry.

During the Treatment Period, to mitigate the risk of infection, subjects will be counseled and reminded of early signs and symptoms of *Neisseria meningitidis* infection. A patient safety card detailing the signs and symptoms of infection with instructions to seek immediate medical attention will be provided to each subject. The card will also describe the subject's participation in the study and the risks of infection associated with inhibition of the terminal complement system. The patient safety card must be carried with the patient at all times while on treatment.

All AEs should be recorded as AEs per Section 12.1 and Section 12.3.

12.2 EVALUATION AND CLASSIFICATIONS

12.2.1 SEVERITY

The investigator should determine the severity of the reported AE by using the NCI-CTCAE (Version 4.0). These criteria will be provided in a separate manual.

For any reported AE not described in the NCI-CTCAE, the following guidelines must be considered for severity evaluation:

Adverse Event Severity

Mild	Symptom(s) barely noticeable to subject or does not make subject uncomfortable; does not influence performance or functioning; prescription drug not ordinarily needed for relief of symptom(s).
Moderate	Symptom(s) of a sufficient severity to make subject uncomfortable; performance of daily activity is influenced; subject is able to continue in study; treatment for symptom(s) may be needed.
Severe	Symptom(s) cause severe discomfort; symptoms cause incapacitation or significant impact on subject's daily life; severity may cause cessation of treatment with study treatment; treatment for symptom(s) may be given and/or subject hospitalized.

12.2.2 CAUSALITY

The causal relationship of the AE to study medication will be assessed by both the investigator and the Sponsor. The assessment of causal relationship to study drug should be evidence-based, and not based on the premise that all AEs are causally related to study drug until proven otherwise. Default categorization of 'related' without supportive evidence for a causal relationship to study drug is generally uninformative and does not contribute to understanding of the safety profile of the drug with respect to the intended population.

Examples of evidence that would suggest a causal relationship between the drug and the AE include occurrence of an AE that is known to be strongly associated with drug exposure (e.g. injection site reaction), or an AE that is otherwise uncommon in the study population. Lack of efficacy of study drug, in isolation, leading to unmasking of underlying symptoms and signs of disease, should not be considered evidence of relatedness.

The causal relationship of each AE is assessed using a binary system with all AEs classified as either ‘related’ or ‘unrelated’.

Related: There is ‘reasonable possibility’ that the drug caused the AE. The AE follows a reasonable temporal association from the time of study drug administration. There is supportive evidence to suggest a possible causal relationship, irrespective of the degree of certainty, between the observed AE and the study drug. There is no alternative more likely explanation for the AE. Lack of study drug efficacy is not considered, by itself, to be evidence of relatedness.

Not Related: Lack of a reasonable temporal association from the administration of the study drug and the occurrence of the AE. There is evidence of an alternative explanation that is more likely as a cause of the AE.

12.3 RECORDING, REPORTING, AND MONITORING

12.3.1 RECORDING AND REPORTING

The investigator must make every effort to properly evaluate all information relevant to the reported AE in such a way that a diagnosis can be confidently made and reported. For example, it is preferable to report “pneumonia” as the AE rather than its symptoms (e.g. “rales” or “fever”) as separate AEs.

When recording and/or reporting AEs or SAEs, the following elements must be included:

- the fulfilled criteria for seriousness as presented in Section 12.1.2
- the severity of the event as defined in Section 12.2.1
- the relationship of the event to study treatment as defined in Section 12.2.2

Actions taken in relation to the AE will be recorded as drug discontinued, drug interrupted, dose reduced, dose increased, concomitant medication, other action (e.g. diagnostic testing), or no action. Any medication given to treat the AE will be recorded separately in the concomitant medication list of the eCRF.

The outcome of the AE will be recorded as date ended, ongoing, or resulting in death with date of death.

12.3.1.1 ADVERSE EVENTS

Pre-existing conditions that are detected prior to administration of the first dose of study drug will be recorded as part of medical history. For all subjects, the AE reporting period will start with the first administration of study drug on Day 1 and will end with the final study visit, after which no new AEs are to be reported. When possible, ongoing AEs assessed as related to the study drug will be followed until resolved or stabilized.

The subjects will be monitored throughout the study for any AEs, including abnormal, clinically significant laboratory values, clinically significant findings at vital signs measurements, spontaneous reports by study subjects, and observations by the study

personnel. Adverse events will be coded using MedDRA after the eCRFs have been monitored and signed by the investigator.

All AEs will be recorded in the eCRF. The investigator will assess and record any AE in detail including the date and time of onset, event diagnosis (if known) or sign/symptom, severity, time course (end date or ongoing), relationship of the AE to study drug, and any action(s) taken. All AEs should be reported separately (i.e. 1 record per event). Reporting of AEs is event-based (i.e. an ongoing event will not be closed until resolved or at the end of study). For the AE description, a diagnosis is preferred over symptoms. If no diagnosis can be made, each symptom will be reported as a separate AE. Abbreviations should be avoided. Descriptive words should be used for ongoing conditions as applicable (e.g. exacerbation of herpes genitalis or worsening of eczema).

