6.3 CLINICAL TRIAL EXPERIENCE WITH RA101495

Clinical trial experience with RA101495 to date includes a single Phase 1 study (RA10145-1001) in healthy volunteers. The study RA101495-1001 was a randomized, double-blind, placebo-controlled, single-ascending-dose (SAD) and multiple-dose (MD) study designed to evaluate the safety, pharmacokinetics (PK), and pharmacodynamics (PD) of RA101495.

The first part of the study (SAD) evaluated a single dose of RA101495 versus placebo at 4 dose levels (0.05, 0.1, 0.2 and 0.4 mg/kg) in separate cohorts. The SAD enrolled 22 subjects; 14 received RA101495 (0.05 mg/kg in two subjects; 0.1, 0.2 and 0.4 mg/kg in four subjects each) and eight subjects received placebo, two per each dose level.

The second part of the study (MD) evaluated 7 daily doses of RA101495 versus placebo at a single dose level (0.2 mg/kg). The MD enrolled six subjects; four received RA101495 and two received placebo.

RA101495 when administered as a single dose and with 7-day repeat dosing displayed consistent and predictable PK that tightly correlated with the PD effect (inhibition of hemolysis and suppression of complement activity).

The plasma concentrations of RA101495 following single-dose SC administration (SAD) showed dose-dependent increases across all dose levels examined (0.05, 0.1, 0.2, and 0.4 mg/kg) (Figure 3). The mean C_{max} ranged from 1010 to 5873 ng/mL across doses. The mean AUC_{0-24} ranged from 21,440 to 112,300 ng* h/mL across doses. The mean half-life ($t_{1/2}$) was consistent across dose levels and ranged from 155.6 to 185.4 hours.

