In the multiple dose (MD) portion of the study, the day 1 mean C_{max} and AUC_{tau} were 2533 ng/mL and 50,010 ng*h/mL respectively, which were consistent with results from the 0.2 mg/kg single-dose cohort over the same post-dose period. Following daily sc administration for 7 days, the C_{max} and AUC_{tau} increased by approximately 2.9 and 3.0-fold respectively (Figure 4). Day 7 time to maximum plasma concentration (median T_{max} = 3.0 hours), total body clearance (mean CL/F = 1.3 mL/h/kg), elimination rate constant (K_{el} = 0.0043h⁻¹) and half-life ($t_{1/2}$ = 161.9 h) were all similar to single dose administration indicating that the absorption and elimination of RA101495 does not change significantly with repeat daily sc administration. The apparent volume of RA101495 distribution (V_z/F) showed some increase with administration of multiple doses of RA101495 (0.2 mg/kg SAD mean V_z/F = 71.4 mL/kg; 0.2 mg/kg MD mean day 7 V_z/F = 311.6 mL/kg). However, the day 7 V_z/F for RA101495 was still less than total body water suggesting that RA101495 does not distribute into the extravascular space upon repeat SC administration.

Figure 3 Mean (SD) Plasma RA101495 Concentrations Over Time by Dose Group Following Single-Dose SC Administration in Healthy Volunteers (Study RA101495-1001)

[figure not shown]
[figure not shown]

Figure 4 Mean (SD) Plasma RA101495 Concentrations Over Time by Dose Group Following Multiple-Dose SC Administration of 0.2 mg/kg for 7 Days in Healthy Volunteers (Study RA101495-1001)

RA101495 demonstrated strong pharmacodynamic effects on terminal complement. RA101495 administered as a single dose achieved rapid dose-dependent inhibition of *ex-vivo* hemolysis as measured by a sheep red blood cell (sRBC) lysis assay (Figure 5). The maximum PD effect was apparent approximately 3 hours after a single dose. The maximal percent inhibition of hemolysis compared to baseline reached $\geq 90\%$ for the 0.1, 0.2, and 0.4 mg/kg single-dose cohorts and 60% for the lowest dose (0.05 mg/kg) cohort. Mean hemolysis levels remained below baseline for up to 2 days in the 0.05 mg/kg cohort, up to 4 days in the 0.1 mg/kg cohort, and for up to 7 days in the 0.2 and 0.4 mg/kg cohorts.

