RA10495 administered for 7-days achieved inhibition of hemolysis that was rapid and sustained at $\geq 95\%$ across the dosing period in all subjects, (Figure 6). The mean percent inhibition of hemolysis compared to baseline reached $>95\%$ beginning at the first time point, 3 hours after dosing on Day 1, and continued throughout 7 days of dosing; all individual subjects showed $\geq 90\%$ inhibition of hemolysis at all time points. At 24 hours after the last dose, inhibition of hemolysis was observed to be $\geq 97\%$ in all subjects. Eight days after the last dose of RA10495, the mean inhibition of hemolysis remained $\geq 56\%$. Two subjects had inhibition of hemolysis $>70\%$ through 8 days after the last day of dosing. Hemolysis returned to pre-dose levels in all subjects within two weeks following the last dose.

Figure 5 Mean (SD) Red Blood Cell Lysis Over Time by Dose Group Following Single-Dose SC Administration in Healthy Volunteers (Study RA101495-1001)

[figure not shown]
[figure not shown]

Figure 6 Mean (SD) Red Blood Cell Lysis Over Time by Dose Group in the Multiple-Dose Cohort Once Daily for 7-Days in Healthy Volunteers in (Study RA101495-1001)

Note: Figure on the right is a duplicate of the figure on the left with an expanded y-axis.

Safety: Across all the SAD cohorts, 7 of the 14 of the subjects treated with RA101495, had adverse events (AEs), which occurred more frequently in the highest dose cohort (0.4 mg/kg). All subjects in the MD (0.2 mg/kg) had at least 1 AE. All AEs resolved. In all cohorts of the SAD and MD, there were no AEs that led to study drug discontinuation. No serious AEs (SAE) or deaths occurred during the study.

In the SAD the most common AEs regardless of causality in subjects who received single-doses of RA101495 were injection site erythema (3 subjects, cohort 4), upper respiratory tract infection (URI) (1 subject, cohort 1; 2 subjects, cohort 4), and headache (2 subjects, cohort 4). Other AEs that occurred in 1 subject each were bronchitis (cohort 1); catheter site phlebitis (cohort 3); fatigue (cohort 4); and back pain (cohort 4). AEs in subjects who received placebo were diarrhea, myalgia, headache, and rash, all in 1 subject each.

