12.3.1.2 SERIOUS ADVERSE EVENTS

Any SAE experienced by the subject from signing the ICF through to 30 days after the last dose of study drug, regardless of severity or causality, must be recorded on the eCRF and SAE Form.

The study site must formally notify the Sponsor of the SAE within 24 hours from the time the study site becomes aware of the SAE. A formal notification must be submitted to the Sponsor regardless of the following:

- severity
- causality
- whether or not the subject received study treatment or underwent study related procedures

The IEC/IRB will be notified as required by local regulations. The investigator will be responsible for submitting the required safety information to the appropriate IEC/IRB, including any safety reports received from the Sponsor as well as any SAEs occurring at his or her site.

The Sponsor, or designee, will prepare any required safety reports for regulatory authorities and all active investigators. These reports will be provided as addenda to the Investigator's Brochure, and the investigator will place these with the brochure.

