12.3.2.1 POST-STUDY EVENTS

Any SAE that was continuing at the time of subject discontinuation or study completion should be monitored by the investigator until resolution or stabilization.

SAEs that occur after the subject discontinues from or completes the study and are considered by the investigator to be related to study treatment or procedures should be reported using the same procedures outlined in Section 12.3.1.2.

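### New non-serious adverse events stop being reported at the final visit, so completers who do not enter the extension have none recorded in the two weeks over which hemolysis returned in Phase 1

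*Protocol*

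**What the plan says.** **Reporting windows.** Protocol 12.3.1.1 opens the AE reporting period at the first dose and says that it "will end with the final study visit, after which no new AEs are to be reported". Protocol 12.3.1.2 records SAEs "from signing the ICF through to 30 days after the last dose of study drug", whatever their severity or cause. Section 12.3.2.1 adds that "SAEs that occur after the subject discontinues from or completes the study and are considered by the investigator to be related" to treatment or study procedures are still to be reported, with no end date. AEs already open are followed up (12.3.1.1, 12.3.2).

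**Where the final visit falls.** Treatment runs from Day 1 to Day 84 (8.2.2), and participation consists of screening plus 12 weeks (8.2). Table 1 shows study drug given at the Week 12/End of Study visit, and its footnotes have all syringes returned then. A subject who stops drug early returns for an End-of-Study Visit (8.4.1), but no interval after the last dose is given.

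**Who continues elsewhere.** The extension is open to completers who are showing benefit. Anyone who withdraws early is barred from it (8.1). Completers who do not roll over go to off-study standard of care (8.2.2).

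**Offset of effect.** Protocol 6.3 reports that eight days after seven daily doses of 0.2 mg/kg, mean inhibition of hemolysis was still at least 56%. It then states: "Hemolysis returned to pre-dose levels in all subjects within two weeks following the last dose". The single-dose half-life "ranged from 155.6 to 185.4 hours"; the Day 7 value is 161.9 h.

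**Analysis.** The TEAE definition (Protocol 13.3.4.1, SAP 3.8.1) has a start but no end.

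**The concern.** The protocol itself treats loss of complement blockade as a hazard: 6.5.1 warns that a modest, brief drop in blockade can bring immediate breakthrough hemolysis and a return of severe symptoms. Its Phase 1 data put that loss within two weeks of the last dose. For a completer who leaves, non-serious AE collection has closed by then, under an explicit instruction not to report.

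Two things are at stake. First, new non-serious hemolysis, hemoglobinuria or infection after stopping would be missing from a study whose first-listed objective is safety and which enrolls at most 20 subjects, so each subject weighs heavily in the tables. Second, the safety tables would mix windows. With no end to the TEAE definition, a serious event on day 10 after the last dose qualifies as a TEAE, while a non-serious event on the same day is never recorded.

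**Working it through.** **1. Reproduce the plan's half-life.** Inputs from Protocol 6.3 and Table 2 (0.2 mg/kg daily, Day 7): elimination rate constant 0.0043 per hour, AUC 151.3 h·µg/mL, half-life 161.9 h, CL/F 1.3 mL/h/kg.

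- ln 2 / 0.0043 = 161.2 h, against 161.9 h stated. Rounding of the rate constant alone allows 159.3 to 163.1 h.
- CL/F = 200 µg/kg / 151.3 h·µg/mL = 1.32 mL/h/kg, against 1.3 stated.

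The figures agree.

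**2. Drug left after the last dose.** Assuming first-order elimination, the fraction left at day d is 0.5^(24d / half-life). The range uses the single-dose half-lives of 155.6 and 185.4 h.

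| Days after last dose | Drug left at 161.9 h | Range | Phase 1 effect (6.3) |
|---|---|---|---|
| 8 | 44% | 43% to 49% | mean inhibition at least 56% |
| 14 | 24% | 22% to 28% | hemolysis back to pre-dose level in all subjects |
| 30 | 4.6% | 4.0% to 6.8% | already reverted |

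Five half-lives are 5 × 161.9 / 24 = 33.7 days (32.4 to 38.6). The effect had gone while about a quarter of the drug was still present, so the interval that matters for returning hemolysis is the two-week offset, not the time to clear the drug.

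**3. Set the windows beside the offset.**

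| Subject | New non-serious AEs | SAEs |
|---|---|---|
| Completer, no extension | about 0 days after last dose | 30 days |
| Early stopper | to the End-of-Study Visit; interval not stated | 30 days |
| Extension entrant | about 0 days in this study; later collection is not in these documents | 30 days |

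The SAE window covers the 14 days with 16 to spare. The AE window covers essentially none of them for a completer who leaves.

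**4. Is 30 days long enough at study doses?** Table 2 predicts a steady-state Cmax of 6.57 µg/mL at 0.1 mg/kg (7.12 at the top of the weight bracket), against 7.29 observed on Day 7 of 0.2 mg/kg. The Phase 1 offset is therefore a fair guide at 0.1 mg/kg. For subjects escalated to 0.3 mg/kg the documents give no steady-state level. If it scaled in proportion to dose (an assumption), it would be 3 × 6.57 = 19.7 µg/mL. The extra time to fall to the same concentration would be log2(19.7 / 7.29) × 161.9 / 24 = 1.43 × 6.75 = 9.7 days, giving about 24 days in all. That is still inside 30.

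**The case against.** The strongest reply is that the protocol already captures what matters most.

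- **Serious hemolysis is counted.** A reader might infer that all return of hemolysis after stopping is lost. The documents do not support that. SAEs are recorded for 30 days whatever the cause, and the SAE definition (12.1.2) includes important medical events needing intervention to prevent a serious outcome. Only new-onset, non-serious events are lost.
- **Five half-lives is not the uncovered risk period.** A reader might take about 34 days as the gap. That figure is not in the documents. It is a convention applied to healthy-volunteer data, and it measures drug presence rather than loss of effect.
- **Early stoppers are not at zero.** Their End-of-Study Visit includes AE recording, chemistry, hematology and urinalysis. Because its timing is not stated, it could fall before or after hemolysis returns.
- **Selective loss is not shown.** A reader might infer that the gap falls on subjects doing worst, with the extension filling it for the rest. Entry is restricted to completers showing benefit, which makes this plausible. But the extension protocol is not available here, and 9.3.1 lists withdrawal reasons unrelated to response.
- **Late injection-site reactions are not supported.** The Phase 1 erythema events were Grade 1 and resolved quickly (6.3).
- **Attribution.** Leavers move to other care, so post-dose events may arise under another drug. Section 12.2.2 also says that lack of efficacy alone is not evidence of relatedness. This objection stands, and it argues for a separate table rather than against collection.
- **Cost.** No contact is scheduled after Week 12, so the change reaches beyond 12.3.1.1. This also stands.

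None of these points supplies a place where a non-serious event in a departing completer would be recorded.

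**Conclusion.** The concern holds in a limited form. For completers who do not enter the extension, new non-serious AEs have about 0 days of collection after the last dose, against 30 days for SAEs, and the uncovered interval contains the two weeks in which hemolysis returned in Phase 1. For early stoppers, who cannot enter the extension, coverage is undefined. Serious events are captured in both groups.

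This rests on three assumptions: that a completer's last dose falls at about the final visit, as the schedule indicates; that an ex vivo assay in healthy volunteers is a reasonable guide to offset in PNH; and that few subjects leave. The documents give no number for the last. Prompt start of other therapy would reduce the number of events but would not change the reporting rule. The gap is worth closing because it comes from a stated rule and closing it is cheap; it does not bear on the primary efficacy analysis.

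**What to change.** - **Protocol 12.3.1.1:** for subjects not entering the extension, end AE reporting 30 days after the last dose, matching 12.3.1.2. Collect the events by one telephone contact at the end of that period.
- **Same contact:** record the start date of any other PNH therapy.
- **Protocol Table 1, 8.2 and 8.6:** add the contact, and align the participation and end-of-study text, which now stop at Week 12 and the last visit.
- **SAP 3.8.1:** tabulate events with onset after the last dose separately from on-treatment TEAEs, flagged by whether other PNH therapy had started. This keeps the on-treatment window the same for subjects who leave and those who roll over.

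**Cost:** wording changes in both documents and one added telephone contact for the few subjects not rolling over. No visit, sample or procedure is added. The limitation is that a call will not detect hemolysis visible only in LDH.
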